7.5.2.2. Time to Clinical (COPD) Exacerbations Short-term Exacerbation Risk (7 days)

For each patient, the following 3 landmark use events will be identified:

- first time in study when had >4 inhalations per day ("low use group")
- first time in study when had >8 inhalations per day ("medium use group")
- first time in study when had >12 inhalations per day ("high use group")

A patient may be included in more than 1 landmark use group (for example, if had >12 inhalations a day any time during study, then on that time or already before he/she also had >8 and >4 a day).

For each landmark use groups, time to CE-COPD within 7 days since the landmark event will be estimated and plotted using Kaplan-Meier plot. The 3 groups will be presented in the same plot, to assess a possible 'dose-response' association, if higher use is associated with shorter time to CE-COPD.

If a CE-COPD has not occurred within 7 days, then that observation will be censored at 7 days or earlier if follow-up had completed/terminated before 7 days elapsed. Note, if CE-COPD occurred on the same date where landmark use happened, then time to CE-COPD will be calculated as 0.

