Clinical Exacerbation of COPD Status: Clinical exacerbation of COPD status is an indicator of whether or not a patient experienced a CE-COPD during study follow-up (Yes, No).

Clinical Exacerbation of COPD Rate: The percentage of patients who experience at least 1 moderate or severe CE-COPD at the end of study follow-up.

Recurrent Clinical Exacerbation of COPD Rate: The percentage of patients who experience more than 1 moderate or severe CE-COPD at the end of study follow-up.

Time to Clinical Exacerbation of COPD: Time, in days, from Study Day 1 to the Date of Symptom Peak plus 1.

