7.5.2.1. Within Patient CE-COPD Analyses

For each CE-COPD event occurring at least 2 weeks after baseline, device-use measures (albuterol use, inhalational flow [MIF], inhalational volume, and time to MIF) will be summarized for each of 2 weeks of interest: first- 'CE-COPD-adjacent week', the week immediately preceding the onset of CE-COPD symptom (ie, day 1 through 7 preceding the date of the CE-COPD symptom onset), and second – 'CE-COPD-Prior Adjacent week', the week preceding that week (ie, during day 8 through 14 preceding the date of the CE-COPD symptom onset). Summary measures of daily and or weekly use will be compared between the two weeks, as proposed below:

Albuterol use measures:

- total number of inhalations in that week
- the maximal daily number of inhalations in that week
- the mean number of daily inhalations (ie, total number of inhalations divided by number of days with number>0)
- occurrence of a single day's albuterol use exceeding 4 inhalations
- occurrence of a single day's albuterol use exceeding 8 inhalations
- occurrence of a single day's albuterol use exceeding 12 inhalations
- number of days when albuterol use exceeding 4 inhalations
- number of days when albuterol use exceeding 8 inhalations
- number of days when albuterol use exceeding 12 inhalations

To note, in this analysis, no inhalation in any day will be taken as a 0 count.

Inhalation flow values parameters:

- maximal daily MIF during the week
- minimal daily time to MIF within a week
- maximal total daily inhalational volume within a week

To note, if no inhalation was taken at a specific day, flow value parameters will be missing and will not be imputed.

Analysis will be based on all patients CE-COPDs for which there are 14 days (or more) prior to the CE-COPD onset, where patient has been on study and CE-COPD free.

Descriptive statistics of use measures in the 'CE-COPD-adjacent week' and 'CE-COPD-Prior Adjacent week' will be presented.

Continuous measures will be compared between the 2 weeks using paired t-test (and Wilcoxon Signed Ranks test) whereas binary patterns will be compared using Mc-Nemar test.

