7.5.2.3. All Days Analysis (Only CE-COPD-free Days)

This analysis will be performed by the data analytics group. Additional details may be specified in a separate report. One possible analysis is presented below:

For each patient, all study days where the patient was CE-COPD free will be the unit of this analysis. There are various ways to summarize albuterol use on this, for example by looking at:

- daily number of inhalations
- albuterol use exceeding 4 inhalations (Yes/No)
- albuterol use exceeding 12 inhalations (Yes/No)

Exploratory analyses using all these patient days can be performed to predict occurrence of CE-COPD event in the next day (for example, using logistic regression). Exploratory predictive analyses will be reported separately.

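### The 7-day landmark plot (SAP 7.5.2.2) does not limit landmarks to days before symptom onset, so albuterol use during an exacerbation already under way can produce an apparent dose-response

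*SAP*

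**What the plan says.** SAP 7.5.2.2 defines three landmarks per patient. The lowest is "first time in study when had >4 inhalations per day" and the highest is "first time in study when had >12 inhalations per day", with >8 in between. From each landmark, time to CE-COPD is shown on a Kaplan-Meier plot, "censored at 7 days or earlier if follow-up had completed/terminated before 7 days elapsed". On same-day events it adds: "Note, if CE-COPD occurred on the same date where landmark use happened, then time to CE-COPD will be calculated as 0". The three curves share one plot, "to assess a possible 'dose-response' association, if higher use is associated with shorter time to CE-COPD". No test is attached.

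Section 7.5.2.2 does not say which date stands for the event. The only definition of time to CE-COPD is in SAP 7.5.1: "Time, in days, from Study Day 1 to the Date of Symptom Peak plus 1".

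The two neighbouring analyses are stricter. SAP 7.5.2.1 is anchored on symptom onset and requires at least 14 prior days "where patient has been on study and CE-COPD free". In SAP 7.5.2.3, "all study days where the patient was CE-COPD free will be the unit of this analysis".

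**The concern.** The study hypothesis (SAP 1.1) is that use rises several days before a moderate or severe CE-COPD and can mark deterioration. A plot bearing on it should count only use that precedes the event. Section 7.5.2.2 does not ensure this. A patient who first exceeds 12 inhalations/day on day 2 of an exacerbation that peaks on day 4 would enter the high-use curve as an event two days after the landmark.

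The distortion is uneven. Most patients who ever exceed 4/day do so on an ordinary day early in the study. Far fewer exceed 12/day on an ordinary day, so a larger share of first crossings of 12 occur because the patient is already exacerbating. The curves can then separate in the order that the plot is meant to detect, with no early-warning signal in the data.

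This matters more because the stepwise prediction models were moved out of the SAP (7.5.3, 20.4) and 7.5.2.3 is offered only as one possible analysis. That leaves 7.5.2.2 as the only fully specified analysis that follows patients forward from use to event. Section 8 plans no sensitivity analysis.

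**Working it through.** **The plan's own figure.** SAP 2.3 expects 91 events (73 to 110) in 360 evaluable patients over 12 weeks, at 1.05 to 1.14 events/year. With the midpoint rate (1.05 + 1.14)/2 = 1.095: 360 × 1.095 × 12/52 = 90.97. The Poisson 2.5% and 97.5% points are 73 and 110, and P(at least 70) = 0.990. The plan's event figures reproduce, so the rate is used below.

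**The correct answer when use carries no warning.** At a constant rate, the 7-day risk after any pre-onset landmark is 1 − exp(−1.095 × 7/365.25) = 2.1%, the same at each threshold.

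**Simulation.** Onset is independent of use, with at most one event per patient, 84 days of follow-up and no dropout. Use is steady until onset, so there is no pre-onset rise. Assumptions not in the documents: mean use 4/day, gamma spread between patients (shape 1.5), Poisson daily counts, use multiplied from onset for 10 days, and peak 3 days after onset. Overdispersion means added day-to-day gamma variation (shape 2).

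| Rise once symptoms start | Event date | >4 | >8 | >12 |
|---|---|---|---|---|
| None | peak | 1.8% | 2.0% | 2.1% |
| ×2, overdispersed | peak | 2.7% | 4.2% | 5.8% |
| ×2.5 | peak | 4.2% | 10.4% | 19.9% |
| ×2, overdispersed | onset | 2.7% | 3.1% | 3.4% |
| ×2.5 | onset | 3.6% | 6.8% | 11.8% |
| ×2.5, starting the day after onset | peak | 3.9% | 9.5% | 18.7% |
| ×2.5, starting the day after onset | onset | 2.3% | 2.2% | 2.0% |
| ×2.5, pre-onset landmarks only | onset | about 2.1% | about 2.1% | about 2.1% |

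With peak dating, the >12 to >4 ratio is 5.8/2.7 = 2.1 in the second row and 19.9/4.2 = 4.7 in the third.

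**Which landmarks cause it.** A second set used mean 3/day, peak 1 to 5 days after onset and use doubled, with the event at peak unless stated:

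| Rule | >4 | >8 | >12 |
|---|---|---|---|
| SAP text | 4.1% | 9.5% | 16.7% |
| Drop time-0 landmarks only | 3.6% | 8.3% | 14.5% |
| Drop landmarks after the peak only | 4.2% | 10.0% | 18.4% |
| Drop landmarks from onset to peak | 1.1% | 1.0% | 1.0% |
| Pre-onset landmarks, event at onset | 2.0% | 2.1% | 2.4% |

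Only dropping the onset-to-peak landmarks removes the gradient. The level then falls to about 1% because the event is still dated at the peak, on average 3 days after onset. Onset must therefore fall within about 4 days of the landmark, and 1.095 × 4/365.25 = 1.2%.

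**At the planned size.** In 400 replicates of 400 patients (mean 3/day, use doubled, peak-dated), the order >4 < >8 < >12 appeared in 93%, or 77% with overdispersion. With pre-onset landmarks and onset dating it appeared in about 20%.

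**The case against.** **The event date is not settled.** The definition in 7.5.1 runs from Study Day 1, not from a landmark, and adds 1 where 7.5.2.2 counts a same-day event as 0. Section 7.5.2.1 uses onset. This stands: peak dating is inferred from the only definition available. It is also a reason to state the date, because the result depends on it.

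**Stronger readings that the documents do not support.**
- A reader might infer that the same-day rule is the whole fault. Dropping it alone leaves most of the gradient under peak dating.
- A reader might infer that the problem is the same whichever date is used. Under onset dating only same-day crossings leak in, and the gradient vanishes if the rise begins the day after onset. With a fixed increase of 6 inhalations/day and onset dating, the pattern was not monotone (9.8/14.8/11.7%).
- A reader might infer that landmarks after the exacerbation create the gradient. They enter as event-free time and slightly dilute it.
- A reader might infer that the plot will show a strong false dose-response. The SAP mentions increased inhaler use only as an example of self-management in the mild definition (7.5.1) and gives no size. With no rise there is no artefact.

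**It is one exploratory plot, with no test, among several analyses.** True, and it limits the severity. Section 7.5.2.1 gives an onset-anchored comparison that would not share the fault, and time-0 events would show as a drop at day 0. The formal test in 7.1.2.3 is less of a safeguard, because its 7-day window is also counted back from symptom peak.

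**Conclusion.** The concern holds in a limited form. As written, 7.5.2.2 lets use during an exacerbation count as a predictor of it, and this can produce an apparent dose-response with no rise before onset. The main route is landmarks between onset and peak when the event is dated at peak. If the event is dated at onset, the same-day rule is the only route left, and it acts only if use has already risen on the onset date.

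The size is conditional. With peak dating and mean use of 4/day it runs from no gradient to a roughly fivefold difference between >12 and >4, depending on the assumed rise and day-to-day variation. The documents fix neither. The simulations show that the plot cannot separate early warning from consequence. They do not show that an observed gradient would be false. For an exploratory, descriptive figure this is a should-fix point.

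**What to change.** In SAP 7.5.2.2:
- define each landmark as the first qualifying day among CE-COPD-free days before symptom onset;
- date the event at symptom onset, as 7.5.2.1 already does;
- start time at risk on the day after the landmark and drop the time-0 rule;
- report, by threshold, the number of patients whose first crossing was on or after onset;
- state whether a crossing after one CE-COPD has ended may serve as a landmark for a later one, since 7.5.1 allows several per patient.

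The cost is SAP wording and one filter in the program. Onset, peak and end dates are already used elsewhere in the SAP (7.5.2.1, 7.1.2.2), so no new data are needed, and SAP 2.4.2 provides for amendments before database lock. The downside is fewer patients in the >8 and >12 curves, and so wider uncertainty there.

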7.5.2.3. All Days Analysis (Only CE-COPD-free Days)

This analysis will be performed by the data analytics group. Additional details may be specified in a separate report. One possible analysis is presented below:

For each patient, all study days where the patient was CE-COPD free will be the unit of this analysis. There are various ways to summarize albuterol use on this, for example by looking at:

- daily number of inhalations
- albuterol use exceeding 4 inhalations (Yes/No)
- albuterol use exceeding 12 inhalations (Yes/No)

Exploratory analyses using all these patient days can be performed to predict occurrence of CE-COPD event in the next day (for example, using logistic regression). Exploratory predictive analyses will be reported separately.

7.5.2.4. Summary Descriptive Statistics of Initial and Recurrent Clinical COPD Exacerbation Rates

Proportion of patients with at least 1 CE-COPD and proportion of patients with recurrent events will be presented.

7.5.3. Predicting Severe CE-COPD/Moderate CE-COPD from Multiple Device-Use-Measures

Predictive analysis will be performed by the data analytics group. Additional details may be specified in a separate report. Exploratory predictive analyses will be reported separately.

8. SENSITIVITY ANALYSIS

There will be no sensitivity analysis performed in this study.

9. MULTIPLE COMPARISONS AND MULTIPLICITY

No adjustment for multiplicity will be applied.

10. SAFETY ANALYSIS

10.1. General

The ITT analysis set will be used for all safety analyses.

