7.1.2. Recording and Reporting of Adverse Events

For recording of adverse events, the study period is defined for each patient as the time period from signature of the ICF to the end of visit 5 ([Table 1](#)). The period for reporting treatment-emergent adverse events is defined as the period after the 1st dose of IMP is administered and until end of visit 5.

All adverse events that occur during the defined study period must be recorded both on the source documentation and in the electronic data capture (EDC) system on the adverse event eCRF, regardless of the severity of the event or the site investigator’s assessment of the relationship of the event to the test IMP. For serious adverse events, the serious adverse event form must be completed, and the serious adverse event must be reported in the EDC system within 24 hours of knowledge of the event (Section [7.1.5.3.1](#)). The investigator does not need to actively monitor patients for adverse events after the defined period.

At each contact with the patient, the investigator or designee must question the patient about adverse events by asking an open-ended question such as "Have you had any unusual symptoms or medical problems since the last visit? If yes, please describe." All reported or observed signs and symptoms will be recorded individually, except when considered manifestations of a medical condition or disease state. A precise diagnosis will be recorded whenever possible. When such a diagnosis is made, all related signs, symptoms, and any test findings will be recorded collectively as a single diagnosis on the eCRF and, if it is a serious adverse event, on the serious adverse event form, which will then automatically result in the distribution of an email to the sponsor.

The clinical course of each adverse event will be monitored at suitable intervals until resolved, stabilized, or returned to baseline; or until the patient is referred for continued care to a healthcare professional; or until a determination of a cause unrelated to the test IMP or study procedure is made.

The onset and end dates, duration (in case of adverse event duration of less than 24 hours), action taken regarding IMP, treatment administered, and outcome for each adverse event must be recorded both on the source documentation and on the eCRF.

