9.2.3. Safety Analysis Set

The safety analysis set will include all enrolled patients who receive at least 1 dose of the test IMP. This analysis population will be used for analysis and summarization of safety data.

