3. ANALYSIS SETS

3.1. Intent to Treat Analysis Set

The intent-to-treat (ITT) analysis set will include all enrolled patients regardless of whether a patient took any IMP. A patient is considered enrolled according to the status reported in the database. This analysis set will be used for endpoint analysis and safety analysis.

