10.4. Adverse Events

All treatment emergent adverse events will be coded using the MedDRA (Medical Dictionary for Regulatory Activities). Adverse events will be included as treatment emergent based on the date of the baseline (ie, the earliest date an ABS eMDPI device was dispensed). Each patient will be counted only once in each PT or SOC category for the analyses of safety. Summaries will be presented for all adverse events (overall and by severity), adverse events determined by the investigator to be related to test IMP (ie, reasonable possibility [Table 5 in Section 7.1.4 of the protocol], defined as related or with missing relationship; overall and by severity), serious adverse events, CE-COPD related adverse events, and adverse events leading to withdrawal from the study, COPD exacerbations by severity, and COPD exacerbations by deterioration.

Patient listings for all adverse events, serious adverse events, and adverse events leading to withdrawal will be presented.

If any patient dies during the study, a listing of deaths will be provided, and all relevant information will be discussed in the patient narrative included in the CSR.

Any adverse event or serious adverse event with a missing start date will be considered treatment emergent.

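### Safety summaries use all enrolled patients and count adverse events from the dispensing date, whereas the protocol requires a first dose for both; events with no prior exposure can therefore be labelled treatment emergent

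*SAP*

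**What the plan says.** **Population.** Protocol 9.7 assigns safety analyses to the safety analysis set, which Protocol 9.2.3 defines: "The safety analysis set will include all enrolled patients who receive at least 1 dose of the test IMP". SAP 3.3 keeps that definition, but no SAP analysis uses the set. SAP 10.1 says instead: "The ITT analysis set will be used for all safety analyses". SAP 3.1 defines that set: "The intent-to-treat (ITT) analysis set will include all enrolled patients regardless of whether a patient took any IMP".

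**Start of treatment emergence.** Protocol 7.1.2: "treatment-emergent adverse events is defined as the period after the 1st dose of IMP is administered and until end of visit 5". SAP 10.4: "Adverse events will be included as treatment emergent based on the date of the baseline", and it explains the baseline date as "the earliest date an ABS eMDPI device was dispensed". SAP 10.4 adds: "Any adverse event or serious adverse event with a missing start date will be considered treatment emergent".

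**Precedence and disclosure.** The SAP introduction gives the SAP precedence where the two documents differ, and promises that differences will be explained in the SAP or in the clinical study report. SAP 20.1 and 20.3 list the move of safety analyses to ITT. The SAP amendment history attributes that move to a decision of the study team and logs the 10.4 change as a clarification. SAP 20 has no entry for the treatment-emergent start date.

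**The concern.** One stated objective is to evaluate the safety of ABS eMDPI use. A treatment-emergent table is normally read as describing what happened after exposure. Under the SAP, a patient can be in the denominator without having inhaled once, and an event can be in the numerator although no dose came before it.

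The plan foresees both situations. SAP 20.2 accepts that as-needed use can mean no use. SAP 5.2 counts enrolled patients who never used the device. SAP 4.2.1 has a rule for patients with no inhalations in study days 1 to 7.

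Other rules add to this. SAP 10.4 treats an event with a missing relationship as related, so an event in a never-dosed patient could be tabulated as both treatment emergent and drug related. SAP 8 plans no sensitivity analysis, so no table on dosed patients would stand beside the ITT one. SAP 5.2 also omits the safety set count that Protocol 9.4.1 included in disposition.

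**Working it through.** **1. The definitions side by side**

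| Item | Protocol | SAP (prevails) |
|---|---|---|
| Safety denominator | Enrolled, at least 1 dose (9.2.3, 9.7) | All enrolled (3.1, 10.1) |
| Treatment-emergent start | After first dose (7.1.2) | First dispensing date (10.4) |
| Patient given a device who never inhales | Not in safety tables | In the denominator; events from dispensing onward count |
| Event between dispensing and first inhalation | Not treatment emergent | Treatment emergent |

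An enrolled patient who was never given a device has no SAP baseline date. That patient's dated events could not be classed as treatment emergent, but the patient would stay in the denominator.

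**2. Effect on a reported percentage (illustration)**

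The plan states no figure for this point. Inputs:
- N = 400 enrolled (Protocol 9.1, SAP 2.3). Check: 360 / (1 − 0.10) = 400, as stated.
- p = 85/316 = 26.9%, the proportion with adverse events in the earlier dose-counter study (Protocol 1.2.2). It serves only as a round starting value. That study used scheduled twice-daily dosing for up to 50 days in asthma and COPD patients from age 4.
- Never-dosed share of 1% to 20%: an assumption, because the documents give none.
- q = proportion of never-dosed patients with an event; k = number of dosed patients whose only event came before the first dose. Both are unknown.

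Reported ITT proportion = (n_dosed × p + k + n_never × q) / 400. The protocol's rules would report p.

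With k = 0:

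| Never dosed | ITT % if q = 0 | ITT % if q = p | Never-dosed patients counted with an event if q = p |
|---|---|---|---|
| 4 (1%) | 26.6 | 26.9 | 1.1 |
| 20 (5%) | 25.6 | 26.9 | 5.4 |
| 40 (10%) | 24.2 | 26.9 | 10.8 |
| 80 (20%) | 21.5 | 26.9 | 21.5 |

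Example, 5% and q = 0: (380 × 0.269 + 0 + 0) / 400 = 25.6%.

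Each patient counted in k adds 1/400 = 0.25 percentage points. With 20 never-dosed patients and q = 0, the dilution is cancelled at k = 20 × 0.269 = 5.4. With 4 never-dosed patients it is cancelled at 4 × 0.269 = 1.1, so two such patients would already push the ITT figure above p. The sign of the net effect is therefore not determined.

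**3. Time counted before exposure (illustration)**

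Share of the 84-day period between dispensing and first inhalation = delay / 84. Assumed delays of 1, 3, 7 and 14 days give 1.2%, 3.6%, 8.3% and 16.7%.

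**The case against.** The strongest reply has four parts.

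*The population change is declared.* This is correct. It appears in SAP 20.1, SAP 20.3 and the amendment history, and Protocol 9 leaves changes to the SAP. A reader might infer that the switch was hidden; the documents do not support that. What stands is that no scientific reason is given. The argument in SAP 20.2, that no use is a legitimate form of as-needed use, is made for the mITT definition and the relation between use and exacerbations. It does not carry over to the safety of a drug that was not taken.

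*Never-users may be few.* Patients must already be using a SABA reliever, must have had an exacerbation in the past 12 months, and are to use the eMDPI as their only rescue agent. That argues for a small share, and the documents do not settle it. A reader might also infer that ITT necessarily understates incidence. The working shows it need not: that holds only if never-users report few events and pre-dose events are rare.

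*The consequence is limited.* There is no control arm and safety is summarised descriptively. SAP 5.2 counts never-users and SAP 10.4 lists all adverse events by patient, so a careful reader could reconstruct much of the picture. This lowers the weight of the point, but it does not make the summary tables match their label.

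*Device records can fail.* SAP 4.6 and 7.2.1 expect unsuccessful downloads. A safety set built only on inhaler data could drop exposed patients, whereas ITT with a dispensing-date start keeps them. This is a fair argument, though the SAP does not make it, and any correction must deal with it.

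**Conclusion.** The two documents conflict on both the safety population and the start of treatment emergence. The SAP prevails, and its version allows events with no prior exposure to be reported as treatment emergent. The population change is disclosed but not justified. The start-date change is presented as a clarification, contradicts Protocol 7.1.2, and is absent from SAP 20; the SAP leaves open that the clinical study report could still explain it.

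The conflict follows from the wording and needs no assumption. The effect on incidence cannot be sized from the documents, and it can go up or down. The percentages in the working rest on assumed never-user shares, assumed delays, and an incidence borrowed from a different setting. They show scale, not a prediction. The main consequence is misattributed events in the safety tables. The exacerbation-prediction objective is not affected. It should be corrected because the correction is cheap.

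**What to change.** - **SAP 10.1:** base the adverse event summaries on the safety analysis set of SAP 3.3. An ITT table may be kept alongside.
- **SAP 10.4:** restore the protocol's start after the first dose, dated from the first inhalation timestamp in the eMDPI. Use the dispensing date only when no timestamp is available.
- **Failed downloads:** treat the patient as dosed unless the returned device or other records show no use, so that exposed patients are not lost from the safety tables.
- **Unexposed events:** list separately the events in undosed patients and those between dispensing and first dose.
- **SAP 20:** enter any remaining departure from the protocol with its reason. If the sponsor keeps the dispensing-date start, that change belongs here.

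The cost is minor extra programming plus the failed-download rule. No new data are needed: the set is already defined, inhalations are timestamped, and all devices are to be returned (Protocol 5.2.3). SAP 2.4.2 requires SAP amendments to be approved before database lock, so the change should be made by then.
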